PROTOCOL: Legal Evaluation for Greater Access to Cancer Care (LEGAL-CARE): A Randomized Pilot Feasibility Trial of a Legal Navigation Program
Version Date: 2-17-2025

Principal Investigator:

[name] MS
Assistant Professor of Medicine
O'Neal Comprehensive Cancer Center
UAB Department of Medicine
Email: [contact]

Research Team and Key Personnel:

[name], MHS
Associate Professor of Medicine
O'Neal Comprehensive Cancer Center, UAB Department of Medicine
Role: Primary Mentor
Email: [contact]

[name], MBA
Professor of Nursing Family, Community & Health Systems
School of Nursing
Role: Biostatistician Mentor, Trial Design and Data Analysis
Email: [contact]

[name]
Assistant Professor of Medicine
O'Neal Comprehensive Cancer Center, UAB Department of Medicine
Role: Collaborator, Qualitative Methodologies
Email: [contact]

[name], BS
Clinical Research Coordinator, Division of Hematology & Oncology, UAB
Role: Patient Interviews
Email: [contact]

[name]
Statistician and Scientist III
Division of Preventive Medicine, UAB Department of Medicine
Role: Research Analyst
Email: [contact]

1. Study Overview

Background and Rationale:

Despite an adept navigation workforce, the regulatory and legal landscape for patients with cancer has become increasingly difficult to navigate. Many barriers faced by patients are entrenched in local, state, and federal policies that require expertise in both social needs and the law. Our group led the first nationwide study investigating the extent to which patients with cancer encounter unmet legal needs related to disability, employment, health insurance, and financial assistance. The Legal Evaluation for Greater Access to Cancer Care (LEGAL-CARE) is a randomized pilot trial to test the feasibility of a legal navigation program. The goal is to address a critical gap in cancer care where patients carry high unmet legal need.

Study Design:

This is a single arm, pilot feasibility trial where 50 recruited patients will receive monthly outreach from a legal navigator over a 6-month period to address legal hardships during their treatment. This study will take place in UAB's medical oncology clinics and include patients aged 18 or older with newly diagnosed advanced stage cancer (stages III or IV) requiring systemic therapy. We hypothesize the legal intervention will be feasible, acceptable and improve patient outcomes.

2. Objectives

Primary Objective:

- **Assess the feasibility of implementing a legal navigation intervention:** Defined as a 70% retention rate and 75% completion of survey completion (at 3 and 6 months) during the 6-month intervention period. Retention and completion rates will be summarized with 95% confidence intervals.

Secondary Objectives:

- Assess the acceptability and appropriateness of implementing a legal navigation intervention
- Collect patient feedback through semi-structured interviews to inform future large-scale trials.
- Explore the impact of the legal navigation program on financial toxicity, quality of life, treatment delays, and healthcare utilization.

3. Study Population

Inclusion Criteria:

- Adult patients aged ≥ 18 years.
- Newly diagnosed with advanced-stage cancer (Stage III or IV).
- Requiring systemic therapy.
- Capable of providing informed consent.

Exclusion Criteria:

- Non-melanoma skin cancer or in-situ tumors.
- Patients with prior hospice encounters within the past year.
- Patients who are unable to participate in study procedures.

4. Study Procedures

Sample size:

As a pilot study, no hypotheses are being tested ¹ (<https://www.nccih.nih.gov/grants/pilot-studies-common-uses-and-misuses>) therefore the study sample size is based on budgetary and logistic considerations to evaluate feasibility goals.

Screening and Enrollment:

Eligible participants will be identified during their oncology clinic visits and provided with information about the trial (**please see Appendix A for patient education materials**). After informed consent is obtained (**please see Appendix B for informed consent**), baseline assessments (noted below) will be conducted, before the legal intervention commences.

Data Collection:

[figure not shown]
- **Baseline:** Demographics, medical history, and baseline survey of legal barriers and financial toxicity (COST-FACIT) and quality of life (FACT-G7) (**Appendices C-D**). You need to describe all the surveys, number of questions, and scoring here.
- **Follow-Up:** Surveys at 3 months and 6 months will assess changes in financial toxicity (COST-FACIT) and quality of life (FACT-G7). Additional surveys at these time points will include Assessing the Feasibility of Intervention (AIM), Intervention Acceptability Measure (IAM), and Feasibility of Intervention Measure (FIM) surveys (**Appendix E**). Information on delays in care (measured in days from first appt in our clinic to first visit for systemic treatment) and healthcare utilization (ER visits, urgent care visits, hospitalizations, ICU-level admissions, and palliative care uptake) will be obtained from the EMR at UAB (**please see Appendix F for EMR collection elements**).
- **Qualitative Interviews:** Conducted at the end of the 6-month intervention period to explore patient experiences and perceptions of legal intervention (**please see Appendix G for interview guide outline**)

Participant Incentives:

Participants will receive \$30 at the end of completion of all surveys, and \$50 for interviews. These incentives may be increased during the study period to maintain participation.

5. Study Intervention

Please see study schema below following details on
Fig – Study Schema

Intervention Overview:

- Participants will receive monthly outreach from a trained legal navigator over a 6-month period. The legal navigator is a lawyer (Juris Doctor, or JD) who will proactively address specific legal barriers the patient may encounter during treatment. Communication will include phone calls (and if requested, virtual consultations) tailored to patient needs. In between legal outreach periods, patients may call the legal navigator team themselves for legal needs that may arise. Legal navigator team will be from Triage Cancer, a

nationwide non-profit organization with a track record of assisting patients with legal barriers following a cancer diagnosis.

- While some of the challenges patients face—such as disability benefits, employment discrimination, health insurance denials, and financial assistance—may also be encountered by social workers, the role of legal navigators is distinct to that of social workers. Legal navigators specialize in interpreting and applying legal frameworks, understanding state and federal regulations, and providing direct legal guidance in areas where legal expertise is critical. For e.g., while a social worker may be able to re-direct a patient at risk of losing housing or financial assistance to additional community resources, a lawyer is able to help the patient interpret legal rights, assist with required paperwork, and provide guidance on navigating legal systems to remove barriers. Similarly, when a patient loses their job, experiences discrimination, or cannot be hired due to a cancer diagnosis and is losing their disability and/or employment benefits, it is the lawyer that is able to help the patient understand their legal rights. You require two completely different skillsets to assist with these, one that a social worker does not carry – that a legal navigator is trained to assist with
- This legal navigation approach ensures that patients receive specialized legal expertise in addressing complex, systemic barriers while complementing, rather than overlapping, social work services.

Intervention Details:

1. Monthly Outreach by Legal Navigator:

- **Frequency and Mode of Communication:**
 - Participants will receive **one scheduled outreach per month** for six months.
 - Communication will be conducted via phone calls, with an option for virtual consultations based on participant preference.
 - Each session will last approximately 30–60 minutes, depending on the complexity of the participant's needs.
- **Discussion Topics:**

During each outreach session, the legal navigator will:

 - Identify new or ongoing legal barriers (e.g., insurance denials, employment disputes, housing issues etc).
 - Review progress on previously identified issues and any actions taken.
 - Provide tailored guidance and resources for addressing specific legal concerns.
 - Offer general legal education on topics such as:
 - **Health Insurance Navigation:** Medicaid/Medicare issues, private insurance appeals, COBRA, and coverage gaps.
 - **Employment Rights:** Understanding FMLA, ADA protections, and wrongful termination.
 - **Disability Benefits:** Applying for Social Security Disability Insurance (SSDI), Supplemental Security Income (SSI), or appealing denied claims.
 - **Financial Assistance:** Locating and applying for programs that provide assistance with medical bills, rent, or utilities.
 - **Estate Planning and Directives:** Creating or updating wills, advance directives, or power of attorney documents.

2. Tailored Legal Support:

- Legal navigators will assess each participant's unique situation and provide step-by-step instructions or direct assistance in resolving legal issues.
- For cases requiring specialized legal expertise or representation, participants will be referred to local resources, including Legal Services Alabama or other partner organizations.

3. Proactive Follow-Up:

- Navigators will follow up with participants regarding unresolved legal issues or new developments. Follow-ups will occur between monthly sessions if required.

4. Between-Session Support:

- Participants may initiate contact with the legal navigator team between monthly sessions for new or urgent legal concerns.
- Legal navigators will respond to patient inquiries within 2–3 business days and prioritize urgent issues such as impending housing eviction or denial of time-sensitive treatments.

5. Documentation:

- All interactions, including participant concerns, recommendations, and resolutions, will be documented in a secure system. This documentation will track intervention fidelity and outcomes.

6. Participant Resources:

- Participants will receive educational materials (print or electronic) summarizing key legal rights and resources discussed during the outreach sessions.

6. Data Management

Data Collection Methods:

- All survey will be collected through REDCap, a secure, web-based application for managing research data.
- All interview data will be managed and analyzed using NVivo, a secure software designed for qualitative data management and analysis
- Information on delays in care (measured in days from first appt in our clinic to first visit for systemic treatment) and healthcare utilization (ER visits, urgent care visits, hospitalizations, ICU-level admissions, and palliative care uptake) will be obtained from the EMR at UAB (**please see Appendix F**)

Data Monitoring:

The principal investigator ([name]), and clinical research coordinators ([name] and [name]) will regularly monitor data quality and completeness. An independent data monitoring committee (DMC) will be established to oversee the integrity of the data and patient safety.

7. Statistical Analysis Plan

Primary Outcome:

- **Feasibility:** Defined as a 70% retention rate and 75% completion of surveys (at 3 and 6 months) during the 6-month intervention period. Retention and completion rates will be summarized with 95% confidence intervals.

Sample size: We will recruit 50 patients to assess intervention feasibility, with no power calculation needed as efficacy is not the primary objective ¹. As a pilot study and consistent with NIH guidance, the sample size is not powered for formal statistical inference but was considered based on examining the feasibility and acceptability of the approach and on refining the intervention design and procedures in preparation for a future larger proposal ².

Analytical approach: Led by the [name] (PI) with input from [name] (co-mentor biostatistician) and implemented by staff analyst, [name] (research analyst/statistician).

Assess feasibility of the intervention: Proportions of: a) eligible approached patients that accept to trial participation; b) proportion of participating patients retained at follow-up; and c) proportion of participating patients completing at least 75% of surveys, will be estimated and

confidence intervals will be computed with simple logistic or probit regression models and inverse link transformations. Descriptive statistics and measures of effect size (e.g., Cohen's d, Cramer's V) will be used to explore association between the proportions of interest and participant sociodemographic characteristics and reported legal barrier types.

Secondary Outcomes:

Explore patient perceptions of legal intervention impact: We will use qualitative methodology therefore biostatistical approaches are not applicable. Sampling for qualitative inquires is sequential and targeted to individuals who can provide insights on the processes under study. Typically, pilot qualitative approaches involve ~20 participants and expect to have a sufficient participant pool to carry out the qualitative inquiry ^{3,4}. This sample size follows qualitative research best practices, ensuring thematic saturation while maintaining feasibility within the study timeline. If thematic saturation is not reached, we will increase this number.

Evaluate trajectory of financial hardship, health-related quality of life, delays in care, and health care utilization: Brief description followed by detailed statistical plan

- **Financial Toxicity:** Changes in COST-FACIT scores will be analyzed using linear mixed-effect models.
- **Quality of Life:** FACT-G7 scores will be analyzed at baseline, 3 months, and 6 months, with adjustments for baseline values.
- **Delays in Care:** Time-to-event analysis will be conducted using Cox proportional hazards models, comparing the time from diagnosis to treatment initiation between the two groups.
- **Healthcare Utilization:** Emergency department visits and hospitalizations will be analyzed using generalized linear mixed models. Results will be presented as mean ratios or odds ratios.

Here we will use repeated measures (baseline, 3 month, and 6 months post-intervention) of survey measures (collected directly) and utilization rates (extracted from EHR). Baseline characteristics and outcomes will be examined with descriptive statistics and measures of effect size. For survey outcome scales (COST-FACIT and FACT-G7), linear mixed-effect models will be fitted with all available data to estimate mean outcomes at each time-point by group. Linear contrasts will be used to estimate mean differences between groups at the follow-up times, adjusted for baseline and 95% confidence intervals will be computed. The models will be of the form $\widehat{Y}_{ij} = \beta_0 + \beta_1 Y_0 + \beta_2 T1 + \beta_3 T6 + \beta_4 LEGAL + \beta_5 T1 \times LEGAL + \beta_6 T6 \times LEGAL + \gamma_i$, where \widehat{Y}_{ij} is the value of an outcome for subject i at time j , β_1 is the coefficient for the baseline outcome value (Y_0), $\beta_0, \beta_2, \beta_3$ are coefficients specific to the reference group (enhanced usual care), $\beta_4, \beta_5, \beta_6$ are coefficients specific to the legal intervention group, $LEGAL$ is a binary indicator of group, $T1$ is a binary indicator for time at 1-month post-intervention, and $T6$ is a binary indicator for 6 months. Linear combinations of model coefficients allow estimation of means by group as well as mean differences. The between-group contrast at 1-month post-intervention (adjusted for baseline) is estimated by $\beta_4 + \beta_5$, and the between-group contrast at 6-months (adjusted for baseline) is estimated by $\beta_4 + \beta_6$. Baseline SDs will be used to rescale the contrasts into standardized measures of effect (Cohen's d). For delays in care, we will use time-to-event analysis methods, such as Cox proportional hazards models, to compare the time from new diagnosis to treatment initiation between enhanced usual care and legal intervention groups. Hazard ratios will be estimated with 95% confidence intervals. For health care utilization measures, generalized linear mixed-effect models will be used. Here, a link-transformation of the expected outcome value is modeled. For discrete count outcomes (e.g. urgent care visits) a default link-transformation is the natural logarithm of the mean, and for binary outcomes (e.g. whether a hospitalization occurred) a default link-transformation is the natural logarithm of the

odds ($odds = p/[1 - p]$). Inverse-link transformations will be used to estimate estimated expected values of the outcomes by group at each time-point. For count outcomes, contrasts are estimated as mean ratios, and for binary outcomes contrasts can be estimated as odds ratios (default) or as relative risks (if the model is fitted with a log-link and a robust standard error). 95% confidence intervals will be computed. We will use SAS (version 9.4M8) and R (version 4.4.2) for the statistical analysis of quantitative data.

8. Safety and Adverse Events

Safety Monitoring:

Any adverse events related to the legal intervention will be recorded and reported to the IRB. Although legal navigation is a low-risk intervention, any significant issues related to stress, patient dissatisfaction, or legal complications will be addressed by the study team.

9. Ethical Considerations

This study will be conducted in accordance with the Declaration of Helsinki and Good Clinical Practice (GCP) guidelines. Informed consent will be obtained from all participants, and confidentiality will be maintained. Study approval is on track to be obtained from the UAB Institutional Review Board (IRB).

10. Dissemination of Results

The results of this trial will be published in peer-reviewed journals and presented at major oncology conferences, including ASCO and/or ASCO Quality Care Symposium. Patient-friendly summaries will also be disseminated through advocacy organizations and local clinics. Collaboration with Legal Services Alabama and Triage Cancer will help ensure broader dissemination to policy-makers and healthcare providers.

11. Timeline

Milestone	Timeline
IRB Approval and Protocol Finalization	Pre Grant
Training Phase	Months 1-3
Recruitment Initiation	Month 4
Completion of Enrollment	Month 16
Primary Data Collection (Baseline, 3-month, 6-month)	Months 4-24
Data Analysis	Months 14-26
Manuscript Preparation	Months 24-30
Dissemination	Months 28-36

12. Conclusion:

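### The protocol calls the trial randomized, then describes a single arm, then plans contrasts with a comparison group that a single arm cannot supply

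*Protocol*

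**What the plan says.** **Randomized.** The title reads "A Randomized Pilot Feasibility Trial of a Legal Navigation Program". Section 1, Background and Rationale, says that LEGAL-CARE "is a randomized pilot trial to test the feasibility of a legal navigation program".

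**Single arm.** Section 1, Study Design: "This is a single arm, pilot feasibility trial where 50 recruited patients will receive monthly outreach from a legal navigator". Section 5, Intervention Overview, makes no distinction between participants: "Participants will receive monthly outreach from a trained legal navigator over a 6-month period". Section 4 goes from consent to baseline assessments to the intervention with no allocation step. Section 7 recruits 50 patients in total and gives no split.

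**Two groups.** In the short outcome list of Section 7, the Delays in Care item plans a Cox model "comparing the time from diagnosis to treatment initiation between the two groups". The detailed paragraph that follows defines a binary LEGAL indicator, takes enhanced usual care as the reference group, and estimates baseline-adjusted between-group differences as b4+b5 and b4+b6. It adds a hazard ratio between the two groups, and utilization outcomes estimated by group with mean ratios or odds ratios. The Financial Toxicity item is compatible with one arm: "Changes in COST-FACIT scores will be analyzed using linear mixed-effect models".

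Two further mismatches lie in the same analysis text. Section 4 says "Surveys at 3 months and 6 months will assess changes in financial toxicity", whereas the Section 7 model has a term for 1 month. Sections 4 and 6 define delay as "measured in days from first appt in our clinic to first visit for systemic treatment", whereas Section 7 starts the clock at diagnosis.

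**The concern.** The number of arms decides whether patients are allocated, how many receive navigation and what can be reported. Staff following the Study Design would navigate everyone. An analyst following Section 7 would then have no comparison group.

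The stake is the secondary objective of exploring impact on financial toxicity, quality of life, treatment delays and utilization. On the single-arm reading, the planned between-group estimates for these outcomes would not exist. What remains is change over time without a control, in patients whose finances and health may change during cancer treatment whether or not a navigator calls. Reporting that under a randomized title would mislead readers about what it shows.

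On the two-arm reading, the primary result also becomes unclear, because Section 7 does not say whether the feasibility proportions apply overall or per arm.

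**Working it through.** The sample size of 50 rests on budget and logistics, so there is no stated calculation to reproduce. The check is whether the stated analysis can be run on the stated design.

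**1. Mixed model.** From Section 7, the fixed part is b0 + b1·Y0 + b2·T1 + b3·T6 + b4·LEGAL + b5·T1·LEGAL + b6·T6·LEGAL. With LEGAL = 1 for everyone it collapses to

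(b0+b4) + b1·Y0 + (b2+b5)·T1 + (b3+b6)·T6.

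Only the bracketed sums and b1 are identified. Adding any constant c to b4 and subtracting it from b0 leaves every fitted value unchanged, yet moves both b4+b5 and b4+b6 by c. Neither contrast is estimable.

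The design matrix was built for 50 patients. The 25:25 split is an assumption, since the protocol gives none. Section 7 lists baseline among the repeated measures and also uses it as a covariate, so both row layouts were tried.

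| Layout | Rows used | Rank (of 7) | b4+b5 and b4+b6 |
|---|---|---|---|
| 25:25 | baseline and two follow-ups | 7 | estimable |
| 25:25 | follow-ups only | 5 | estimable |
| Single arm | baseline and two follow-ups | 4 | not estimable |
| Single arm | follow-ups only | 3 | not estimable |

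With follow-up rows only, two ranks are lost even with two arms, because T1 + T6 equals the intercept column. That is a separate flaw of parametrization. The single arm costs 3 ranks in the first layout (7 − 4) and 2 more in the second (5 − 3).

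**2. Cox model.** At a log hazard ratio of 0, the information for group is the sum over events of p(1 − p), where p is the share of patients at risk who are in the LEGAL group.
- Single arm: p = 1 at every event, so the information is 0.
- Assumed 25:25 with all 50 patients starting treatment: at most about 50 × 0.25 = 12.5. Simulation gave about 12.

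**3. What a single arm can deliver.** The 95% half-width for mean change, in baseline SDs and with equal SDs at both times, is t(0.975, n−1) × √(2(1−ρ)) / √n. The correlation ρ is not in the protocol and is assumed.

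| n | ρ = 0.3 | ρ = 0.5 | ρ = 0.7 |
|---|---|---|---|
| 50 | 0.336 | 0.284 | 0.220 |
| 35 (70% of 50) | 0.406 | 0.344 | 0.266 |

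**4. What two arms would deliver.** With 25 per arm, the unadjusted 95% half-width for a between-group Cohen's d is 1.96 × √(2/25) = 0.55. At 70% retention (17.5 per arm) it is 1.96 × √(2/17.5) = 0.66. If retention were reported per arm, the half-width at 70% would be 1.96 × √(0.7 × 0.3/25) = 18.0 points, against 12.7 points with all 50.

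**The case against.** The best case against a high ranking is that little of importance is touched. The protocol says that no hypotheses are tested, and the primary outcome is retention and survey completion. Those proportions, and the acceptability, appropriateness and feasibility scales, need no comparator. Section 4 still contains a drafting note, so the group language may be residue from another design that an edit would cure. That limits the harm. It does not remove the contradiction, because the number of arms is basic to any protocol.

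The study schema and the appendices are not available here and might describe a control condition. The absence of an allocation step, arm sizes and a description of enhanced usual care is therefore a statement about the available text only. A control group shown there would still contradict the single-arm statement.

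For utilization, Section 7 speaks of values by group and then of contrasts, without saying outright that the contrasts are between groups. That is the natural reading. Ratios between time periods would remain estimable in one arm.

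The 1-month term and the time origin do not depend on the number of arms. They add no weight to this point, but they sit in the text that has to be rewritten and need correction under either design.

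A separate SAP could replace the models, but it could not reconcile the protocol's own title, Study Design and Section 7.

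**Conclusion.** The concern holds and must be fixed. The protocol describes two incompatible designs, and the analysis it plans cannot be run on the design stated in Section 1. With one arm, both mixed-model contrasts, the group hazard ratio and any between-group utilization ratio cannot be estimated at any sample size. This follows from the stated model and needs no assumption beyond all 50 patients being navigated. The two-arm comparisons rest on an assumed 25:25 split, and the precision of within-patient change rests on the assumed correlations and equal SDs.

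The damage is confined to exploratory outcomes if the trial is single arm. The available text does not settle which design is intended, although the operational text in Sections 1 and 5 supports one arm.

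**What to change.** The sponsor should state the number of arms and make the title, Sections 1 and 5 and all of Section 7 agree.

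**If single arm:**
- Remove the randomized label from the title and background.
- Delete the LEGAL terms, the group contrasts, the hazard ratio and the reference to enhanced usual care.
- For COST-FACIT and FACT-G7, one workable model is Y = b0 + b1·T3 + b2·T6 + patient random effect, with baseline as an outcome row. It has full rank (3 of 3). Y0 then drops out as a covariate, so the FACT-G7 item on baseline adjustment must be reworded too.
- Report mean change with 95% intervals, also divided by the baseline SD.
- Report utilization by period from a time-only count or binary model.
- Describe time to treatment without a hazard ratio.
- Label all changes as uncontrolled.

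**If two arms:** correct Sections 1 and 5, state the allocation method, arm sizes and control condition, and say whether feasibility is judged overall or per arm.

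**Either way:** replace the 1-month term with the 3-month survey, and use one time origin for delays throughout.

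**Cost.** The single-arm route is essentially rewording of the protocol and any SAP, with no change to patients or visits. The consent form, education materials and EMR element list were not available and should be checked for the same wording and for the dates collected. The price is that no between-group effect size can be claimed. The two-arm route changes conduct: allocation and control content must be added, and fewer than 50 patients may receive navigation if the total stays at 50.

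### The COST-FACIT and FACT-G7 model uses the baseline score both as an outcome row and as a covariate, so between-group intervals are too narrow and single-arm change is biased under baseline-related dropout

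*Protocol*

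**What the plan says.** Protocol Section 7 introduces the survey analysis with: "Here we will use repeated measures (baseline, 3 month, and 6 months post-intervention) of survey measures". It then says that "linear mixed-effect models will be fitted with all available data to estimate mean outcomes at each time-point by group".

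The printed equation has an intercept (beta0), the baseline score Y0 (beta1), two time indicators (beta2, beta3), a group indicator LEGAL (beta4), two group-by-time terms (beta5, beta6) and a random patient intercept. Beta1 "is the coefficient for the baseline outcome value". The first time variable "is a binary indicator for time at 1-month post-intervention" and the second "is a binary indicator for 6 months". The between-group contrasts are beta4+beta5 and beta4+beta6, with 95% confidence intervals and rescaling to Cohen's d.

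The Quality of Life bullet in the same section says: "FACT-G7 scores will be analyzed at baseline, 3 months, and 6 months, with adjustments for baseline values".

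Section 1 (Study Design) describes a single arm of 50 patients who all receive the intervention.

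**The concern.** An intercept with one indicator for each of two follow-ups leaves baseline as the reference visit. Together with the listed repeated measures and the use of all available data, this makes baseline scores outcome rows. The same equation then predicts each of those rows from Y0, which is the same number. Such rows carry no information about how well baseline predicts follow-up, yet they pull beta1 towards 1 and shrink the variance that the model attributes to patients.

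This is not a detail that can be left to a separate analysis plan, because the protocol prints the equation, its coefficients and its contrasts. It is the only model specified for financial toxicity and quality of life. Since the pilot tests no hypotheses, the intervals and standardised effects are what a larger trial would take from it.

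**Working it through.** The protocol gives no SE or interval width to reproduce. Taken from it: N = 50, the visits, the equation and the contrasts. Assumed: SD 1, one common correlation rho between visits, and 25 + 25 patients where two groups are considered.

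**1. Slope on baseline.** With complete data, beta1 is the slope of a patient's three-visit average on Y0, which is (1 + 2·rho)/3. The true slope of follow-up on baseline is rho. At rho = 0.6 the model gives 0.733 instead of 0.60.

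**2. Variance the model sees.** The residual variance is s² = 1 − rho. Given Y0, the patient average varies only through the two follow-ups, with variance 2(1 − rho)(1 + 2·rho)/9. Setting this equal to tau² + s²/3 gives a patient variance tau² = (1 − rho)(4·rho − 1)/9. At rho = 0.5 this is 0.056. With follow-up rows only it would be rho(1 − rho) = 0.25.

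**3. Between-group contrast at 6 months.** The estimate is D6 − beta1·D0, where D6 and D0 are the group differences in mean score at month 6 and at baseline.
- Model SE ≈ √[(2/25)(tau² + s²)]
- Actual SD ≈ √[(2/25)(1 − 2·beta1·rho + beta1²)]

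At rho = 0.5 the model SE is √(0.08 × 0.556) = 0.211 and the actual SD is √(0.08 × 0.778) = 0.249. Random-intercept REML simulations (3,000 trials per setting) agree:

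| rho | beta1 | Formula: SE / SD | Simulated: SE / SD | 95% interval covers |
|---|---|---|---|---|
| 0.3 | 0.53 | 0.239 / 0.278 | 0.239 / 0.279 | 91.1% |
| 0.5 | 0.67 | 0.211 / 0.249 | 0.211 / 0.244 | 91.7% |
| 0.7 | 0.80 | 0.170 / 0.204 | 0.170 / 0.207 | 89.6% |
| 0.8 | 0.87 | 0.141 / 0.171 | 0.141 / 0.170 | 90.4% |

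With 30% missing at 6 months and 15% at the first follow-up, the simulated SE / SD is 0.244 / 0.303 at rho 0.5 (coverage 89.6%) and 0.194 / 0.242 at rho 0.7 (89.1%). Across all settings the SE is 13% to 20% too small.

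Over the same settings, follow-up rows only with Y0 and one time indicator cover 94.7% to 95.4%. Baseline as outcome only, with a common baseline mean, covers 94.3% to 95.4%.

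**4. Single arm, N = 50, group terms removed, rho = 0.6.**
- *Change from baseline, complete data.* Y0 is constant within a patient and cancels. The SE is √(2 × 0.4/50) = 0.126 with or without it, and coverage over rho 0.3 to 0.8 is 95.0% to 95.7%.
- *Change from baseline, dropout related to baseline (assumed about 30% by month 6).* The inflated slope over-corrects for the retained patients' different baseline scores. Bias is about 0.05 SD and coverage 91% to 92%. Without Y0, bias is 0 to 0.01 SD and coverage 94% to 95%.
- *Model-based 6-month mean.* Here tau² + s² = 0.062 + 0.4 = 0.462, so the SE is √(0.462/50) = 0.096, against a sampling SD of 1/√50 = 0.141. Coverage is 83%, and 95% without Y0. Follow-up rows only with Y0 gives √(0.64/50) = 0.113 and 87.5% to 89%.

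**5. Baseline rows dropped from the printed form.** With two groups, the two time indicators sum to the intercept and the two interactions sum to LEGAL, so the rank is 5 of 7 columns. Single coefficients such as beta2 or beta4 are not unique, but beta4+beta5 and beta4+beta6 remain estimable.

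**The case against.** Several objections stand in whole or in part.

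- **The follow-up-only reading.** A reader might infer that without baseline rows the model cannot be estimated, so that neither reading is usable. The documents do not support that. The protocol asks for "Linear contrasts will be used to estimate mean differences between groups at the follow-up times, adjusted for baseline and 95% confidence intervals". Those two contrasts survive the rank deficiency, and removing one time indicator with its interaction gives a valid model. What counts against this as the intended reading is that the text lists baseline among the repeated measures and the FACT-G7 bullet analyses it as a visit.
- **All intervals too narrow?** Not so. Single-arm change from baseline with complete data is the same with or without Y0.
- **The 83% figure.** It does not isolate this fault. Part of the shortfall comes from conditioning on the observed baseline scores, and follow-up rows with Y0 as covariate share that part.
- **Single arm against two groups.** Section 1 has one arm, so LEGAL is constant and neither contrast is estimable. That conflict is more basic and forces a rewrite anyway. It is a separate matter, though: removing the group terms or adding a comparison group both leave Y0 on the two sides of the equation.
- **Importance.** The primary outcome is a set of feasibility proportions, which this does not touch. The survey outcomes are exploratory and the sample is not powered for inference. This lowers the severity but does not make the equation right.

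**Conclusion.** Wrong as written, of moderate severity. Baseline is both an outcome row and a covariate in the only model for COST-FACIT and FACT-G7.

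With two groups, the between-group SE is about 13% to 20% too small and nominal 95% intervals cover about 89% to 92%. In the single arm that Section 1 describes, the harm is narrower. Change from baseline is biased by about 0.05 SD when dropout depends on baseline, and the 6-month mean has too small an SE as an estimate of the population mean, only partly because of this fault.

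The even split, the correlations, the amount of missing data and the link between dropout and baseline are assumptions. The protocol gives none of them; its 70% retention target only makes 30% loss a plausible scenario. The double use of baseline and the rank result follow from the text alone.

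**What to change.** State one role for the baseline score and use the same form for both scales.

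- **Single arm, as in Section 1:** keep baseline, 3 and 6 months as outcome rows, delete beta1·Y0 and all LEGAL terms, and report change from baseline as the two time coefficients.
- **If a comparison group exists:** either use that form with group terms, or use only the 3- and 6-month rows with Y0 as covariate, one time indicator and its interaction with group. Restate the contrasts to match.

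In the same edit, reconcile the 1-month label on the first time indicator with the 3-month survey, and align the FACT-G7 bullet with the chosen form. The cost is rewording one paragraph and one bullet in Section 7, with no new data and no extra patients.
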